**Timeline**

---

**(1) Eligibility Screening: (Approximately 60-90 minutes, in person)** The Eligibility Screening will consist of inclusion questionnaires, communication questionnaires, and audiologic assessment. Both the participant and communication partner can be present for this visit and will both complete all testing for the Eligibility Screening.

If the participant and/or communication partner has had an audiologic assessment within the past year, then they are welcome to bring those results with them to their Eligibility Screening. If both the participant and communication partner have hearing assessment results from within the past year, then both of them will not be required to complete an audiologic assessment in the laboratory. If only one or neither member of the dyad has had an audiologic assessment within the past year, then the one member or both will complete an audiologic evaluation within the laboratory prior to visit 1.

Inclusion Questionnaires
	
Hearing health and history questionnaire: Participants will be asked questions regarding their hearing health history in an interview style format. If done remotely, this can be completed via phone or video chat.
 
MoCA: with a score <math>\geq 24</math> (within normal limits): The Montreal Cognitive assessment is a cognitive screening test designed to detect mild cognitive impairment. It requires approximately 10 minutes and assesses short-term recall, visuospatial abilities, executive function, attention, working memory, language, and orientation to time and place. This may be administered remotely via phone/video chat or in-person.
	
Data Collection Time: 20-30 minutes
	
Questionnaires have no risk involved for the participant

Communication
	
Communication Participation Item Bank
	
Data
	
Questionnaires


Questionnaires
	
(CPIB): This measure was designed for hearing and communication across different communication disorders and life situations. Items probe the extent to which the participant’s condition interferes with a range of interpersonal speaking situations.
 
Unidimensional Relationship Closeness Scale (URCS): This questionnaire describes the relationship between the participant and their communication partner.
 
Speech Spatial and Quality Scales (SSQ-12): a self-assessment of speech understanding, spatial hearing, and other qualities of sound on a scale ranging from 0 to 10, with higher scores towards 10 suggesting little to no difficulty.
 
Hearing Handicap Inventory for Adults (HHIA): self-assessment scale containing 25 items of two subscales (emotional and social/situational). The assessment measures perception of emotional aspects and social limitations perceived by the individual with hearing loss.
	
Collection Time: 30-40 minutes
	
have no risk involved for the participant

Audiologic Assessment
	
Otoscopy: Standard clinical procedure to look into the ear to observe the eardrum and ear canal.
 
Audiometry (Air & Bone Conduction): Study audiologists will complete an audiologic evaluation, including: pure-tone air conduction thresholds at 0.25, 0.5, 1, 2, 3, 4, 6, 8 kHz; pure-tone bone conduction thresholds at 0.5, 1, 2, 4 kHz; speech discrimination in quiet and in noise. If medically necessary, tympanometry, a measure of middle ear function, may be performed. This procedure would be necessary if one or more of the following conditions are met: the eardrum is not clearly visible with otoscopy (whether by scarring on the eardrum, earwax obstructing some view of the eardrum, or any other condition that makes viewing the
	
Data Collection Time: 15-20 minutes
	
Otoscopy, audiometry, and QuickSIN are standard clinical procedures with no risk to the participant.

	
eardrum difficult), and/or if the patient complains of pressure or fullness of one or both ears, and/or if there is a conductive component on the audiogram and the eardrum appears normal.
 
QuickSIN: This is a clinical auditory test that consists of low-context sentences in a background of 4 talker babble. The speech is set to an audible level and the noise is gradually increased. Research participants verbally repeat as much of the sentence as possible.
		
--	---	--	--

**(2) Visit 1: (Approximately 100-120 minutes)** Visit One will consist of the hearing aid fitting and verification, and the Diapix Conversation Analysis both in aided and unaided conditions for the participant. The communication partner will be present and participate in the Diapix Conversation Analysis with the participant. Only the participant will be fit with hearing aids.

A pair of the listed hearing aids will be fit on participants comparing two settings; (1) a self-fit setting made by participants following the manufacturer’s recommendations, and (2) an audiologist-fit setting. All participants will undergo both an initial self-fit and then complete testing with the audiologist-fit settings. Participants will be tested with or without the audiologist-fit settings at random with an equal allocation among participants within testing materials. Due to the within-subject nature of this trial, a blinded trial is not possible. However, every effort will be made to avoid comparisons of self-fit and audiologist-fit algorithms to minimize participant and researcher bias in verbal and written communication with the participants.


Hearing Aid Fitting & Verification
	
Hearing Aid Fitting: The participant will be instructed on how to insert the hearing aid into their ear(s) and will follow step-by-step instructions on a hearing aid application on a cell phone to fine-tune the hearing aid to their preferred settings. Then, the audiologist will made additional adjustments using hearing aid verification process to fine-tune the hearing aid to the participant’s audiologic pure tone thresholds.
 
Hearing Aid Verification: Hearing aid verification involves the use of a soft probe tip microphone into the ear canal with the hearing aid situated in the ear canal correctly. The participant will hear sentences of soft, average, and loud intensity as the software is measuring the output gain of the hearing aid
	
Data Collection Time: 15-30 minutes
	
Hearing aid fitting and verification are standard clinical procedures.
 
Minimal to no risk for hearing aid fitting: patient may perceive hearing aids as louder than anticipated, and adjustments will be made to ensure the hearing aids are programmed to a comfortable listening level that is not hazardous to hearing.

--	---	---	--

	
and comparing it to the recommended NAL-NL2 targets based on the participant's audiometric pure tone thresholds.
		
Minimal to no risk for hearing aid verification: during verification, participant will have a very soft, flexible probe tube microphone placed in the ear to measure the output of the hearing aid as it is sitting in the participant's ear. The probe tip may feel "ticklish" or may feel odd in the participant's ear canal. Efforts will be made to ensure the participant is comfortable during all procedures.
 
Participant is welcome to take a break at any time without consequence.


Diapix Conversation Analysis
	
Diapix Conversation Analysis: Consists of derived measures including proportion of trouble sources, proportion of unsuccessful repairs, proportion of complex repairs: video and audio recording will be collected from each participant/communication partner dyad at two timepoints: pre-fitting (unaided), and wearing the hearing aid (aided). Conversation data will be collected at one of our research sites, or remotely. If conversation data is collected in a participant's home or remotely, study staff will survey the environment removing (or positioning recording equipment to avoid recording) any personally identifying or sensitive information (i.e., mail with addresses, pictures of young children or unconsented individuals, personal
	
Data Collection Time: 70-90 minutes
	
Minimal to no risk: Minimal risk of boredom or minimal fatigue with task.
 
Participant is welcome to take a break at any time without consequence.

	
documents) prior to recording. If in person, the study team will replace these items once data have been collected as part of the session clean-up routine. Conversation data will be collected using standardized Diapix conversation tasks. The participant-communication partner pair will be seated approximately 3-5 feet apart with a barrier between them and will be instructed to describe standardized picture stimuli from to their partner (partner is not able to see the primary speaker’s picture but has a companion picture of their own). The goal of the conversation task is to have the partner use the primary speaker’s description to identify up to 12 objects that are missing on their picture, but present on the primary speaker’s picture. The Diapix sampling method is a standard approach for collecting conversation samples (Baker & Hazan, 2011). The Diapix pictures are freely available to the research and clinical community and can be found through the Northwestern Online Speech/Corpora Archive and Analysis Resource (OSCAAR; Kendall, 2010; http://oscaar.ling.northwestern.edu/).
		
--	--	--	--

**(3) Visit 2 (Approximately 60 minutes):** The second visit will consist of tasks of executive functioning (Stroop Task, Flanker Task) and a physiological measurement (pupillometry) to measure listening effort during the Rapid Recall Task (RRT). Only the participant will attend visit 2.


Tasks of Executive Functioning
	
Stroop Task: This is a measure that assesses reaction time and conscious versus automatic visual processing. This test takes approximately 5 minutes to administer. Participants are instructed to read black text that indicate the names of colors, as quickly as possible. The second part of the assessment includes participants seeing colored lines, and they are instructed to name the colors on the page as quickly as they can. The third part of administration is the participant will then be given a list of color names, where they say the color of each word, not read the text itself. For example, if the word “yellow” was written in
	
Data Collection Time: 10-15 minutes
	
Minimal to no risk: Boredom and minimal fatigue may occur during testing. Participant is welcome to take a break at any time without consequence.

--	--	---	--

	
green ink, the correct response is “green”. Participants are timed for each of the three segments.
 
The Flanker Test: We will administer two tasks tapping this interference control ability and compute a z-score aggregate to obtain a stable estimate. In the arrow flanker task, participants see a > or < sign, surrounded by two > or < signs on either side (i.e., >>>>, <<<<). Their task is to focus on the middle sign and decide whether that sign is pointing to the left or the right as quickly and as accurately as possible by pressing one of the two buttons (left or right). The reaction time difference between the compatible (i.e., >>>>) and incompatible stimuli (i.e., <<<<) will be used to index interference control ability. In the letter flanker task, participants will see either a letter G or H in the middle, surrounded by two Gs or Hs on either side (i.e., HHHHH, GGHGG). Participants’ task is to focus on the middle letter and determine as quickly and as accurately as possible whether it is a G or an H. Again, the reaction time difference between the compatible (i.e., HHHHH) and incompatible (GGHGG) stimuli will be used as the index of interference control ability.
		

Pupillometry & Recall Repeat Task (RRT) (Data Collection Time: 30-40 minutes)
	
Pupillometry: a measurement of pupil size, is correlated with task difficulty in a variety of research focused on cognition. Task difficulty, or listening effort, during conversation is a useful measure of how effortful auditory processing is to the participant. The participant will be asked to rest their chin on a fixed chin rest and press their forehead on a cushioned support rest. Participant will be asked to fixate on a dot during the duration of testing. Testing will be completed with the Recall Repeat Task (RRT) during pupillometry recording. Pupillometry data collection will measure dilations of the pupil and record these dilations using EyeLink software.
 
Recall Repeat Task (RRT): an auditory only speech-in-noise task that assesses auditory
	
Data Collection Time: 30-40 minutes
	
Minimal risk to participants: Minimal to no risk include boredom with the task and minor fatigue from sitting still and maintaining a stable head position during the task. Participant is welcome to take a break at any time without consequence.

	
working memory and reported listening effort by participants. The participant is presented with a list of pre-recorded sentences that they are asked to repeat back and to recall 15 seconds after repeating back a list of 6 sentences. After the participant recalls the sentences heard, they are asked to rate on a scale of 1 to 10 how effortful they found the listening situation to be and are asked to provide an estimated time of how long they are willing to spend listening to speech-in-noise condition. Responses are recorded by the examiner in the testing interface, which is not visible to the participant.
		
--	---	--	--

For this study, we will not need to access any participant’s pre-existing HIPAA or PHI protected medical or health information or data. Also, we will not need to access any secondary data that is not HIPAA protection or contains PHI.

We will not use mobile apps for data collection during this study.

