**11.0 Consent Process:**

Prior to enrollment, potential participants will have a hearing and cognitive test with authorization by a screening consent form. These tests will allow us to exclude potential participants from enrolling in the study who are ineligible based upon their hearing or cognitive status. If participant is eligible based upon their screening results, they will be enrolled in the study with separate consent. These 45-minute tests are built into the study design of the eligibility tasks, and do not require additional visits.

If a participant is not eligible to participate based upon the screening consent, they can authorize future contact with the consent's optional element and authorize the lab to retain the screening audiogram.

Consents may be obtained via hard copy or digitally via RedCAP, depending on participant preference. In either case, all subjects will provide their consent to study procedures to the investigator or her research assistants. An unlimited amount of time will be provided to the participant to ensure they have adequately reviewed the consent form and all questions have been addressed by study staff. Following the subject's opportunity to read the consent document, study staff will review each section with participant to clarify the study or any procedure and ensure understanding. Additionally, consent forms may be provided to a potential research participant before a study visit is scheduled so they may take extra time to review before committing to participation.

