## 15.0 Audio/Video Recording/Photography

All visits will be audio and video-recorded to determine the effectiveness of the study treatment.

Audio/video recording of testing:

- Identified with a unique identifier (no personal health information).
- Audio/video data will be stored on a dedicated server managed by the Northwestern University School of Communication Hearing Aid Laboratory (HALAB).
- Audio/video data will be uploaded directly to the HALAB Research Group server via a secure Northwestern University network.
- Audio/video data will be accessible only by trained research staff involved with this protocol.
- Audio/video data will be stored in compliance with Northwestern policies [https://research.northwestern.edu/sites/research/files/policies/Research\\_Data.pdf](https://research.northwestern.edu/sites/research/files/policies/Research_Data.pdf).
- Data will be stored indefinitely post final data analyses OR Conversation recordings will be stored indefinitely on the HALAB Research group server.

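### A within-subject design does not make blinding impossible: the scorers of the Diapix recordings can be masked to condition and order

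*Protocol*

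**What the plan says.** The statement on blinding is in section 8.0, Visit 1, in the paragraph on the two fitting settings: "Due to the within-subject nature of this trial, a blinded trial is not possible". No other reason is given. The next sentence offers one mitigation: every effort will be made to "avoid comparisons of self-fit and audiologist-fit algorithms" in order to "minimize participant and researcher bias in verbal and written communication with the participants".

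The Diapix Conversation Analysis entry for the same visit describes its outcomes thus: "Consists of derived measures including proportion of trouble sources, proportion of unsuccessful repairs, proportion of complex repairs". They come from audio and video recordings of each dyad at two timepoints, one before fitting without aids and one with the aids worn.

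Section 15.0 gives the purpose of recording: "All visits will be audio and video-recorded to determine the effectiveness of the study treatment". It adds that each recording carries a unique identifier, and on access: "Audio/video data will be accessible only by trained research staff involved with this protocol". Nothing in the protocol says that scorers are kept unaware of condition or recording order.

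**The concern.** The reason given is not a reason against blinding. A within-subject design means that each participant meets every condition. It does not determine what a person scoring a recording afterwards must know. As worded, the sentence applies to the whole trial and so sets aside a safeguard that is available for the Diapix outcomes.

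Those outcomes matter here. The protocol names no primary outcome, but the only precedent cited in section 3.0 for the sample size is a Diapix study. Deciding what counts as a trouble source, and whether a repair is unsuccessful or complex, very probably requires judgement. A scorer who knows which recording is aided could classify talk differently in a consistent direction, and that shift would appear in the results as a device effect.

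**Working it through.** **Who can and cannot be masked, from the protocol's own description**

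- *Participants:* they know whether they are wearing aids, and they make the self-fit themselves through a phone application. Masking fails because of the intervention.
- *Fitting audiologist:* makes the later adjustment and sees the verification. Masking fails for the same reason.
- *Scorers of stored recordings:* neither the intervention nor the within-subject design requires them to know the condition.

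**Does the stated mitigation reach the scorers?** It covers communication with participants, and only the self-fit versus audiologist-fit comparison. It covers neither scoring nor the unaided versus aided contrast on which the Diapix timepoints are built.

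**Do the identifiers mask the scorers?** Section 15.0 (unique identifier) and section 18.0 (subject ID in the file name) protect privacy. Neither is said to hide condition or order. Because the unaided recording always precedes fitting, a scorer who knows the order knows the condition.

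**Number of recordings.** Section 3.0 plans 30 dyads and expects 20 at the end. With one recording per timepoint (an assumption), there are at least 2 × 20 = 40 or 2 × 30 = 60.

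**Why more dyads do not help.** If the true mean paired difference is δ and the scorer shift is b, the mean paired difference estimates δ + b at any sample size.

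**Illustration.** The protocol gives no test, alpha, SD or bias size, so there is no figure of its own to reproduce. Assume a two-sided 5% paired t-test, δ = 0, and a shift of d SD of the paired differences. The test statistic then follows a noncentral t with n − 1 degrees of freedom and noncentrality d√n. The false-positive rate is P(|T| > t₀.₉₇₅,ₙ₋₁).

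| Assumed shift d | d√20 | Rate, 20 dyads | d√30 | Rate, 30 dyads |
|---|---|---|---|---|
| 0 | 0 | 5% | 0 | 5% |
| 0.1 | 0.45 | 7% | 0.55 | 8% |
| 0.2 | 0.89 | 14% | 1.10 | 19% |
| 0.3 | 1.34 | 25% | 1.64 | 36% |

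Simulation with 200,000 trials per non-zero cell agrees to within about 0.001. The rate reaches 10% at d = 0.153 with 20 dyads and d = 0.123 with 30.

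**Partial masking.** If masking halved an assumed shift of 0.2 to 0.1, the rate would fall from 14% to 7% (20 dyads) or from 19% to 8% (30 dyads). The halving is also an assumption.

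**The case against.** The strongest reply is about scope. The sentence sits in a paragraph comparing self-fit with audiologist-fit, and the mitigation after it concerns the same comparison, so its natural subject may be participants and session staff. For them the conclusion is right. On this reading the rest is missing detail: who codes, from what material and under what masking are matters often left to a SAP or coding manual, which is not shown.

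This does not dispose of the point. The protocol is not silent; it declares a blinded trial impossible, for a reason that does not support the claim. A SAP that specified masked scoring would contradict that sentence, so the correction belongs in the protocol.

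Other parts of the objection stand:

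- That the Diapix measures need rater judgement is an inference, because the protocol does not describe the coding. That a scorer would shift counts consistently is a possibility, not a finding.
- The bias sizes are assumed. The table shows how a shift would act, not how large it is in this trial.
- Video may show the aids and the talk may reveal the condition, so masking could be incomplete.
- The low cost is a judgement; the protocol gives neither costs nor staff numbers.
- Masked scoring leaves participant expectation and the fixed unaided-first order untouched.

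**Conclusion.** The concern holds. The stated reason is invalid, and the plan as written leaves the Diapix outcomes open to observer bias that paired data cannot separate from a hearing-aid effect. The conclusion is limited to the Diapix outcomes and rests on the very probable inference that they involve rater judgement. The size of any bias is unknown. Under the stated assumptions, shifts of 0.1 to 0.3 SD of the paired differences would raise a nominal 5% error rate to between 7% and 25% with 20 dyads, or between 8% and 36% with 30. The case for correction does not depend on any one of these values: the sentence is wrong on its face, and a partial safeguard is available.

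**What to change.** Replace the sentence with wording such as:

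> Participants and fitting staff cannot be masked because of the nature of the intervention. Diapix recordings will be copied under random codes without condition or order labels. They will be coded in shuffled order by existing study staff who are not told the condition and, where staffing allows, were not involved in that dyad's session. Audio, or video with the ears obscured, will be used where feasible.

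The recordings are already planned (section 15.0). The work would fall to the trained research staff of section 15.0 or the research assistants mentioned in section 11.0. No visit, procedure or participant is added. The cost is relabelled copies and a shuffled coding list for about 40 to 60 recordings, some scheduling, and more effort if ears are obscured. Audio-only coding may lose visual cues. The protocol does not show whether coding and testing staff can be separated, so that element is conditional. The result would be an assessor-masked Diapix comparison, not a fully blinded trial.

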**Exclusion criteria of participant/communication partner:**

1. Clinically significant unstable or progressive medical conditions, or conditions which, in the opinion of the investigator(s) places the participant at unacceptable risk if he or she were to participate in the study
2. History of unresolved communication difficulties following another neurological problem (i.e., stroke or brain tumor), neurodevelopmental disorder (i.e., Down's syndrome), or head/neck cancer
3. Diagnosis of dementia or cognitive impairment
4. Positive history of major psychiatric disorder (i.e., schizophrenia, significant untreated depression)
5. Co-enrolled in other intervention studies targeting hearing, language, or communication strategies
6. History or current fluctuating hearing loss
7. Evidence of conductive hearing loss
8. Current active hearing aid wearer (defined as wearing hearing aid(s) at least 4 hours a day for most days within the past year)
9. Current active hearing aid wearer within 30-day trial period of purchased hearing aids from a licensed provider

For the purposes of test validation and calibration, we may also enroll a small group (n=10) of listeners with normal hearing, defined as pure-tone thresholds of 20 dB HL or less at octave frequencies between 250 and 4000 Hz. With the exception of having normal hearing, those participants will follow the inclusion and exclusion criteria described above.

We will not include any other special populations (adults unable to consent, individuals under 18 years of age, pregnant women, or prisoners or other detained individuals).

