### **3.0 Sample Size:**

A study evaluating eye gaze and communication ability with hearing loss during the Diapix Conversation Analysis (Davis et al, 2017; DOI: [10.21437/AVSP.2017-3](https://doi.org/10.21437/AVSP.2017-3)), found a significant difference in their group of 19 dyads. Participants had hearing loss. To our knowledge, this is the only study with the most comparable methods to our study.

We will plan to collect data on 30 dyads (30 participants and 30 communication partners). We anticipate having 20 dyads by the end of our study, with 30 dyads set for room for dropouts. For visit 1 of the study, both parties will be required to attend the sessions. For visit 2, the communication partner does not need to attend. Historically less than 10% of participants drop out of studies within our lab. However, due to COVID19, we anticipate the possibility of higher-than-average dropouts.

The sample will consist of adults at least 18 years of age and older and their communication partner also be at least 18 years of age or older to participate.

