**Approach:**

This is a within-subjects design and participants will wear hearing aids only during scheduled lab visits. Participants will **not** take the hearing aids outside the lab or home with them. The expected total duration of the study is 2-4 visits based on the typical timing of assessments and procedures. The range of duration of scheduling and visits will occur at times convenient for the participants. Although the study is sectioned into three visits (Eligibility, visit 1, and visit 2) participants can merge visits together (such as Eligibility and visit 1) into one visit, or split up a visit (i.e., such as changing visit 2 to two separate visits) based on the participant’s schedule and convenience.

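### The unaided Diapix run is labelled pre-fitting, so order is confounded with aided versus unaided; the settings randomisation probably does not reach this contrast

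*Protocol*

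**What the plan says.** All of this is in the protocol.

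- **Design (section 8.0, Approach).** "This is a within-subjects design and participants will wear hearing aids only during scheduled lab visits".
- **Visit 1 content (section 8.0, Timeline).** The visit includes "the Diapix Conversation Analysis both in aided and unaided conditions for the participant". This sentence sets no order.
- **Diapix timepoints (Visit 1 table).** Recordings are made "at two timepoints: pre-fitting (unaided), and wearing the hearing aid (aided".
- **Settings compared (Visit 1).** "A pair of the listed hearing aids will be fit on participants comparing two settings": one self-fit, one audiologist-fit. Both are aided.
- **Randomisation (Visit 1).** "Participants will be tested with or without the audiologist-fit settings at random with an equal allocation among participants within testing materials".
- **Sequence (Visit 1).** "All participants will undergo both an initial self-fit and then complete testing with the audiologist-fit settings".
- **Sample size (section 3.0).** 30 dyads are planned and 20 are expected at the end. The precedent cited is "A study evaluating eye gaze and communication ability with hearing loss during the Diapix Conversation Analysis"; it is not tied to aided versus unaided.
- **Optional extra group (section 2.0).** "For the purposes of test validation and calibration, we may also enroll a small group (n=10) of listeners with normal hearing". The protocol does not say that this group repeats Diapix.

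The visit text and table list fitting before Diapix, but as components of the visit and not as a test order. No section states a different Diapix order, a practice run, or how picture sets are assigned to the aided and unaided runs.

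**The concern.** An aid can be worn for testing only once it has been fitted. If the unaided run comes before fitting, it comes before the aided run in every dyad, and condition and order become one variable. The same two people do the same kind of picture-description task twice. Familiarity with the task or with each other's descriptions could favour the second, aided run; boredom or fatigue, which the protocol rates as minimal, could count against it. The direction is unknown, so the bias cannot be called conservative.

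At stake is the only contrast for which the protocol names an unaided condition. Diapix takes 70-90 minutes of a 100-120 minute visit. The test schedule fixes the problem, so an analysis plan cannot repair it without added assumptions, and more dyads do not remove it.

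**Working it through.** The protocol states no order effect, SD, test, alpha or power, so there is no figure of its own to reproduce. The order-effect sizes, the paired t-test and the 5% level below are assumptions. The 20 and 30 dyads are from section 3.0.

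**1. Two conditions, one aided setting.** Let τ be the hearing-aid effect and π the change from first to second run. With unaided first in every dyad, each paired difference (aided minus unaided) has mean τ + π. A model with 20 dyad effects, an aided term and a period term has 22 columns but rank 21, because the aided and period columns are identical. With a 10/10 split of orders the rank is 22 of 22.

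**2. Both settings tested, unaided always first.** Take 20 dyads with unaided in position 1 and the two settings in positions 2 and 3, 10/10.
- Free period factor: rank 23 for 24 columns, so aided versus unaided is still not estimable.
- Linear order trend: rank 23 of 23, so it is estimable.
- Precision, in within-dyad residual SD, for mean aided minus unaided: with no trend term the variance is (1 + 1/2)/20 = 0.075, SE 0.27. With the trend, the aided runs lie on average 1.5 positions after the unaided run, and the slope per position has variance 2/20 = 0.10. The variance becomes 0.075 + 1.5² × 0.10 = 0.300, SE 0.55. The standard error doubles.

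**3. Illustrative false-positive rate, fixed order, one aided setting.** With τ = 0 and π = d SD of the paired difference, the paired t statistic is non-central t with n − 1 df and non-centrality d√n. For n = 20 the critical value is 2.093; at d = 0.3 the non-centrality is 0.3 × √20 = 1.342 and rejection is 24.7%.

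| Order effect (SD of paired difference) | 20 dyads | 30 dyads |
|---|---|---|
| 0.05 | 5.5% | 5.8% |
| 0.1 | 7.1% | 8.3% |
| 0.2 | 13.6% | 18.5% |
| 0.3 | 24.7% | 35.5% |
| 0.5 | 56.5% | 75.4% |

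More dyads make it worse, because the bias stays and the standard error shrinks.

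**4. Random order, two conditions.** Unaided-first dyads estimate τ + π. Aided-first dyads estimate τ − π − L, where L is any carryover from wearing the aid into a later unaided run. The mean of the two is τ − L/2.
- With L = 0 the order effect cancels. In 100,000 simulated trials with π from 0.05 to 0.5 SD, absolute bias was at most 0.0009 SD and rejection 4.98-5.14% (10/10).
- With carryover the bias is L/2. L of 0.1, 0.2, 0.3 or 0.5 SD gives 5.5%, 7.1%, 9.7% or 18.5% rejection (10/10, 18 df).
- Random order has the smaller bias when |L| < 2|π|.

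**5. Could the optional normal-hearing group supply the order effect?** Even if it repeated Diapix, n = 10 gives a 95% half-width of 2.262/√10 = 0.72 SD, wider than any order effect in the table.

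**The case against.** **The order rests on one label.** True. The fixed order follows from the word pre-fitting alone; elsewhere the protocol says only that both conditions are tested. The point is therefore conditional on the label being followed. No other section gives a different order.

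**The randomisation sentence may be wider.** Read literally, testing without the audiologist-fit settings could include unaided testing. A reader might infer that the randomisation certainly excludes it. The text does not settle that: the preceding sentences define the comparison as self-fit versus audiologist-fit, which makes the narrower reading likelier but not certain. On the wider reading, random order contradicts the pre-fitting label and the two statements still need reconciling.

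**An analysis might rescue the contrast.** A reader might infer that no analysis could ever separate the effects. That is too strong. It holds if one aided setting is tested. If both are tested in random order, an assumed form such as a linear trend makes the contrast estimable, at twice the standard error. The protocol does not say which case applies.

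**A pre-fitting baseline is a legitimate choice.** It is, and random order has its own carryover risk. The documents give neither effect's size, so they do not prove which design is less biased. What stands is that the limitation should then be stated.

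**The harm may be small.** Fatigue is rated minimal, breaks are allowed and visits may be split. At 0.05 SD the rejection rate barely moves. No primary contrast is named, and the self-fit versus audiologist-fit comparison is not affected by this point, so a reader should not infer that the trial as a whole is compromised.

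**Conclusion.** The point holds in conditional form and should be fixed; confidence is medium because it depends on one label and an ambiguous randomisation sentence. If the label is followed, order is confounded with aided versus unaided in Diapix. With one aided setting this cannot be undone from these dyads; with both settings in random order it can be undone only under an assumed form for the order effect, with a loss of precision.

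The size is unknown. Under the assumed test with 20 dyads and no true benefit, false-positive rates run from close to nominal for a very small order effect to more than half of trials at 0.5 SD. These figures show sensitivity and do not estimate what will happen in this trial. The conclusion is confined to the aided-versus-unaided Diapix contrast.

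**What to change.** 1. State whether the aided Diapix run uses one setting or both. Separately, reconcile the sentence sending all participants from self-fit to audiologist-fit testing with the sentence saying testing is at random, and say whether the latter includes unaided.
2. Preferred: remove pre-fitting from the definition of the unaided run, complete the fitting first, and randomise the Diapix order with unaided included. With one aided setting, use a 1:1 two-order list (15 and 15 of 30 dyads). With both, use a balanced three-condition list; the six possible orders would take five dyads each.
3. Balance picture sets across all conditions, unaided included, and include period in the analysis.
4. If a hearing-aid-naive baseline is wanted, keep the order and state that aided versus unaided is a before-after comparison that cannot be attributed to the hearing aid alone.

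**Cost.** Wording and an order list; no added visit. Fitting plus Diapix takes 15 + 70 = 85 to 30 + 90 = 120 minutes in either order, against a stated 100-120 minutes. With two conditions and 20 dyads, the detectable difference at 80% power moves from 0.660 to 0.662 SD (10/10), or 0.676 SD if dropout leaves 12/8; if 20 of 30 complete at random, the split is 12/8 or closer in 95% of cases. These precision figures do not cover a three-condition design.

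**Downside.** The unaided run would no longer precede all exposure to amplification, and with two conditions any carryover biases the contrast by half its size.
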